## **9.2 Bias Minimization**

All subjects meeting the specified eligibility criteria will be enrolled in the study until all spots are filled up.

## **9.3 Planned Analyses**

The clinical study report will contain only information necessary to prove this phenomenon.

Statistical analysis will include the VAS forms from each procedure which will be used to show there is laser analgesia and potentially cavity preparations can be performed by using the laser without the need to give injection anesthesia first. The VAS form is used to show how much pain they are in and if any. All patient data will remain anonymous during analyses to maintain patient confidentiality.

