## SYNOPSIS

Title of Study	Clinical Study of Laser Analgesia in Cavity Preparations using the Er,Cr:YSGG Laser
Objectives	To show there is laser analgesia. Restorative dental procedures potentially can be performed without needle injection first.
Planned Number of Subjects and Duration of Involvement	The planned number will be forty-eight patients. The duration will last till all patients are done.
Patient Population	Patients included in the study are adults 19-65 years old who had at least two cavity preparations of the same type, with the same approximate size lesion. Excluded patients include children, people with language barriers, pregnant women, immune compromised patients compromised (No bronchitis, no sinus infection, no ear infection, ect...), patients with heart disease, uncontrolled hypertension, cardiac arrhythmia, and patients whose teeth amalgam restorations were in close proximity to the lesion.
Investigational Product Name	Clinical Study of Laser Analgesia in Cavity Preparations using the Er,Cr:YSGG Laser
Methodology Overview	The study involves using the Er,Cr:YSGG Laser to perform cavity preparation without giving any injection anesthesia. This study is going to be done to show there is laser analgesia.

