## 3 STUDY OBJECTIVES

The principal objective of this study is to prove the phenomenon of laser analgesia. Traditionally before a cavity preparation is performed, the doctor will use local anesthetic (Needle Injection) before using rotary instrument to do a cavity preparation. The study involves using the Er,Cr=YSGG Laser to perform cavity preparation without giving any injection anesthesia. VAS (Visual Analog Scale) will be used to have patients rate the laser

cavity preparation procedure to show there is laser analgesia. On each patient subject that has two similar size cavities of the same classification, either Class I or Class V, on similar teeth. Two different laser protocols will be used. One includes Low Level Laser Therapy (LLLT) to condition the pulp producing analgesia before using higher power to perform the cavity prep. The other protocol will skip the LLLT setting and prepare the cavity with the higher power to perform the cavity prep. The design of the study is to find out if there is laser analgesia and if LLLT makes a difference in providing better analgesia. The VAS forms from each procedure will be used to show there is laser analgesia and potentially cavity preparations can be performed by using the laser without the need to give injection anesthesia first.

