## 4 STUDY OVERVIEW

### 4.1 Study Approach

[figure not shown]
**Treatment.** Preconditioning and cavity preparation are done using the Er:Cr:YSGG laser, Waterlase MD (mfg: Biolase Technology Inc, Irvine CA), and the gold hand piece with an MG6 fiber tip, trunk fiber, contra-angle hand piece. *Preconditioning.* Preconditioning is preformed using laser desensitization. One tooth will be randomly selected, and preconditioning will be performed using LLLT on the tooth with minimal tooth ablation. The LLLT settings that will be used for preconditioning are 0.25 Watts, 50 Hz, 0% water, 0% air, H mode. Following this a fiber-optic tip will be aimed perpendicular to the surface of the cervical portion of the tooth, ensuring that a 2mm distance will be maintained between the end of the fiber optic tip and the surface. The fiber-tip will be used to generate a 2mm line. The cavity on the second tooth will be prepared for without laser preconditioning. *Lesion Preparation – small preparations.* Small preparations are to be performed as follows. The Waterlase MD is set to 4.5W, 15 Hz, 65% air, and 60% water and the cavity is prepared according to the preferred technique. If patients indicate sensitivity, the procedure will be halted, patients fill out the VAS form and anesthetic will be offered. For patients who refuse anesthetic, the procedure will be continued at the same settings. *Lesion Preparation – small to medium preparations.* Small to medium preparations will be performed as follows. The Waterlase MD will be set to 2W, 15 Hz, 65% air, and 60% water and the cavity will be prepared according to the preferred technique. If patients indicate sensitivity, the procedure will be halted, patients fill out the VAS form and anesthetic will be offered. For patients who refuse anesthetic, the procedure will be continued at the same settings.

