#### **Preparation of Lesion:**

- A. Laser ablation- Small Preparation
  - a. Waterlase MD settings: 4.5W, 15Hz, 65% air, 60% water
  - b. Prepare cavity preparation using preferred technique
  - c. If the patient indicates sensitivity,
    - Halt the procedure
    - Have the patient mark the VAS form,
    - Offer anaesthetic; if refused, continue using the same settings
- B. Laser ablation- Small and Medium Preparation
  - a. Waterlase MD settings: 2W, 15Hz, 65% air, 60% water
  - b. Prepare cavity preparation using preferred technique
  - c. If the patient indicates sensitivity, either
    - Halt the procedure

- Have the patient mark the VAS form,
- Offer anaesthetic; if refused, continue using the same settings

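### The hedged no-injection statement rests on VAS forms, which do not measure it; completion without injection is not an outcome, and finishes under injection fall outside the study

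*Protocol*

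**What the plan says.** Section 3 (Study Objectives) names the VAS forms as evidence for two things, analgesia and the possibility of working without an injection: "The VAS forms from each procedure will be used to show there is laser analgesia and potentially cavity preparations can be performed by using the" (the rest of the sentence concerns laser work with no injection beforehand). Section 9.3 (Planned Analyses) repeats this link: "Statistical analysis will include the VAS forms from each procedure which will be used to show there is laser analgesia and potentially cavity preparations can" (ending in the same way). The same section says what the form records: "The VAS form is used to show how much pain they are in and if any".

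The Synopsis carries the statement as part of the objective, "Restorative dental procedures potentially can be performed without needle injection first", but does not mention VAS.

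Section 4.1 describes what happens when a patient signals: "If patients indicate sensitivity, the procedure will be halted, patients fill out the VAS form and anesthetic will be offered". It goes on: "For patients who refuse anesthetic, the procedure will be continued at the same settings". The workflow in Section 7.1 agrees: "Offer anaesthetic; if refused, continue using the same settings".

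Section 6.1.2 (Safety issues) says that after a pain signal an injection is available as an option to finish, and that this will be outside the study. The VAS explanation in Section 4.1 adds one further analysed quantity, the number of hand raises.

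**The concern.** The protocol names its evidence for the no-injection statement, and that evidence measures something else. The VAS runs from no pain to the worst pain the patient has felt. Nothing in the document ties a point on that scale to needing an injection. The two can part in both directions: a patient in pain may refuse the anaesthetic and finish, and a patient with a modest score may accept it.

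The result that would answer the statement is produced at the chair. After each signal the patient accepts or refuses, so each completed preparation ends with or without an injection. No section makes this an outcome, and Section 6.1.2 sets the injected finishes aside. The report could therefore present the statement as supported without counting injections.

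**Working it through.** **The plan's own figure.** Section 9.1 uses a finite-population formula for a proportion with c = 1.96, N = 50, p = 0.50 and A = 0.025:

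n = 1.96² × 50 × 0.25 / (0.025² × 50 + 1.96² × 0.25) = 48.02 / 0.99165 = 48.42.

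This reproduces the stated value. The 1.69 printed in the numerator of the worked line would give 36.00, so it is a misprint that does not affect the result. The formula sizes the study for a proportion, yet no proportion is among the stated outcomes. I take 48 patients with two teeth each, hence 48 teeth per laser protocol.

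**What VAS can show.** Take one laser protocol with 48 teeth: 36 never signal and score 0 (Section 4.1 assigns an overall zero when no hand is raised), and 12 score 40 mm. These counts and scores are assumptions. Let the 12 either all accept or all refuse the injection. Section 6.1.2 can be read as removing the injected teeth, or only the part done under injection.

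| Reading of Section 6.1.2 | 12 accept (25% injected) | 12 refuse (0% injected) |
|---|---|---|
| Injected teeth removed | 36 teeth, mean VAS 0/36 = 0 mm | 48 teeth, mean VAS 480/48 = 10 mm |
| Teeth kept with the score of 40 | 48 teeth, mean VAS 480/48 = 10 mm | 48 teeth, mean VAS 480/48 = 10 mm |

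On the first reading, the scenario with more injections gives the better VAS. On the second, VAS does not separate the two. A third reading, removal of the whole patient, takes out at least the same 12 teeth.

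**What a completion rate would show under the present text.** If injected teeth are removed, the rate among retained teeth is 36/36 = 100%, with an exact 95% lower limit of 0.025^(1/36) = 90.3%. With all 48 teeth in the denominator it is 36/48 = 75%, exact 95% CI 60.4% to 86.4%. The 100% would arise whatever the true rate.

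**What hand raises add.** An injection is offered only after a signal, so the number of teeth with at least one raise is an upper limit on the number injected. In the illustration that limit is 12 in both scenarios, which fits anything from 0 to 12 injections. If removed teeth also drop out of the hand-raise count, the accept scenario shows no raises in 36 teeth and the limit is lost.

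**Keeping the teeth does not by itself repair VAS.** The overall VAS is marked after the preparation ends (Sections 4.1 and 7.1). For a tooth finished under injection that mark may reflect pain felt under anaesthetic.

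**Precision of the direct outcome.** With 48 teeth per protocol and assumed counts, the exact 95% CIs are:
- 24/48 = 50%: 35.2% to 64.8%
- 36/48 = 75%: 60.4% to 86.4%
- 43/48 = 90%: 77.3% to 96.5%
- 48/48 = 100%: 92.6% to 100%

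**The case against.** The principal objective in Section 3 is to prove laser analgesia, and Sections 1, 2.2 and 3 add whether LLLT improves it. VAS is a direct measure for both. The no-injection line is worded with a potentially wherever it appears, so it can be read as an implication and not a tested hypothesis. This stands, and it limits the point to that statement. A reader might infer that the trial's main question cannot be answered with VAS; the documents do not support that.

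A reader might also infer that the Synopsis rests the statement on VAS. It does not; only Sections 3 and 9.3 make the link.

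The wording is "potentially cavity preparations can be performed by using the laser without the need to give injection anesthesia first", and starting without an injection is not the same as finishing without one. True, but every study preparation starts without one by design. On the narrow reading no data could bear on the statement, so only completion makes it informative.

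Hand raises are already analysed and are a closer proxy than VAS. That stands as an upper limit, subject to which teeth are retained.

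Section 9.3 says the analysis will include VAS, which is not exhaustive, and an analysis plan or the case report form may add more. One therefore cannot say that acceptance goes unrecorded, because the form is not shown. But the protocol itself names VAS as the evidence and itself sets injected finishes aside; those two statements need correcting where they stand.

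Finally, a reader might say that following the plan yields the same 10 mm mean whether 0% or 25% are injected. That holds only if injected teeth stay in with their scores. If Section 6.1.2 removes them, the means are 0 and 10 mm, in the wrong order.

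**Conclusion.** The point holds for the hedged no-injection statement in Sections 3 and 9.3. The evidence named for it does not measure it, and the outcome that does is neither stated nor protected from exclusion. If Section 6.1.2 removes injected teeth, completion without injection among retained teeth is 100% by construction. In the illustration, mean VAS is then 0 mm with 25% of teeth injected. The 36/12 split and the score of 40 are assumptions; the document gives no expected injection rate. The 100% result depends on the removal reading of Section 6.1.2 but not on those figures. The mismatch between VAS and the statement holds on any reading. It does not invalidate VAS as a measure for the analgesia and LLLT questions.

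**What to change.** - **Sections 3 and 9.3:** tie the no-injection statement to a per-tooth yes/no outcome, cavity preparation completed without injection anaesthesia.
- **Data collection:** record for each tooth whether an injection was accepted, if the case report form does not already do so.
- **Section 6.1.2:** reword so that every treated tooth stays in the denominator and an injected tooth counts as not completed without injection. Table 1 has data returned or destroyed when a patient withdraws before data collection is complete; report the number of such patients separately.
- **Analysis:** give the proportion with an exact 95% CI for each laser protocol, and compare the two teeth within patient with a paired method such as McNemar's test.
- **VAS and hand raises:** keep them for the analgesia and LLLT questions.

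The cost is at most one form item and wording changes in three sections. The accept-or-refuse decision already occurs, so clinical care does not change. The change should be made before enrolment, because unrecorded decisions may not be recoverable. A small downside for the sponsor is that the result may look less favourable than a low mean VAS.

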# **10 ADVERSE EVENT REPORTING**

## **10.1 Non-Device-Associated Adverse Events**

Adverse events occurring during the enrollment period should be documented by the Investigator in progress notes, but will not be collected or analyzed unless considered serious by the Investigator.

Serious adverse events (SAEs) encountered during study enrollment will be documented by the Investigator and reported immediately upon discovery. SAEs are defined under current Good Clinical Practice (cGCP) guidelines as events that result in one or more of the following:

- life-threatening illness or injury;
- permanent impairment of a body structure or a body function;
- medically necessary in-patient hospitalization;
- medical or surgical intervention necessary to prevent permanent impairment to body structure or function; or
- fetal distress, fetal death, or congenital abnormality.

SAEs will be reported using an Unanticipated Adverse Device Effects (UADE) form, which serves the dual role of capturing pertinent SAE information per industry guidelines and capturing device information pertinent to medical device standards. Other serious events that affect the rights, safety, or welfare of subjects must also be documented on the UADE form and must be reported immediately to the Investigator's IRB according to that IRB's policies.

All adverse events that happen during this study will be treated seriously according to the appropriate policies, which should be none, will be documented in the patient's medical record using the UADE form and will be reported immediately to the Investigator's IRB according to that IRB's policies. Also, a Follow-up will be implemented for AEs that cause interruption or discontinuation of the study, or those that are present at the end of study treatment as appropriate.

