### **10.2.2 Reporting of device-associated adverse events**

Monitoring of adverse events (AEs) is critical to the patient's safety (i.e., human subjects protection) and data integrity.

Per this investigational plan, study subjects are not expected to experience any device-associated adverse events.

If instrument operators or research staff employed by the Sponsor experience any adverse events associated with study-specific use of the investigational device, the events will be processed according to the standard complaint investigation and handling policies, which may include recording of the event in the product's design history file.

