# **11 RISK ANALYSIS**

## **11.1 Potential Risks of the Investigational Product and Clinical Investigation**

The procedures used in this study are experimental. However, there is no more of a risk during this study than there would be during any other cavity preparations performed by [name]. If you are having any pain during the procedure, we ask that you please signal us by raising your hand. We will stop the procedure and use injection anesthesia as an option to finish the procedure. You may decline to answer any or all questions and you may terminate your involvement at any time if you choose with no penalty.

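### Section 10.1 gives two incompatible rules for non-serious adverse events, and 10.2.2 sets a handling route only for staff, so whether such events in subjects are captured and can be summarized is undetermined

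*Protocol*

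**What the plan says.** Protocol section 10.1, headed as covering non-device-associated events, contains two general rules.

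- **First paragraph.** "Adverse events occurring during the enrollment period should be documented by the Investigator in progress notes", but they "will not be collected or analyzed unless considered serious by the Investigator".
- **Last paragraph.** "All adverse events that happen during this study will be treated seriously according to the appropriate policies, which should be none"; each "will be documented in the patient's medical record using the UADE form and will be reported immediately to the Investigator's IRB", in line with that board's policies. Follow-up is added for events that interrupt or end participation or are still present at the end of treatment.

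Between these, 10.1 defines serious adverse events, sends them to the UADE form with immediate reporting, and adds a catch-all for other serious events bearing on subjects' rights, safety or welfare.

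Section 10.2.1 defines a UADE, which is a serious event or problem. Section 10.2.2 calls adverse event monitoring critical, then states that "study subjects are not expected to experience any device-associated adverse events". The only handling step it gives begins "If instrument operators or research staff employed by the Sponsor experience any adverse events".

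Section 11.1 says of the trial: "The procedures used in this study are experimental".

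**The concern.** The two paragraphs of 10.1 tell the investigator different things about the same event. Under one, a non-serious event stays in the clinical notes and never enters the study data. Under the other, it generates a UADE form and an immediate report. Section 12.5 permits deviations only in emergencies, so the investigator cannot simply choose a rule.

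The natural place to settle device-associated events in subjects is 10.2.2, but that section expects none and moves on to staff. An expectation of no events is not a collection rule. If events are not collected, the expectation cannot be checked.

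At stake is the non-serious safety record of a procedure the protocol itself calls experimental. A statistical analysis plan could specify a table of adverse events, but it could not restore events that the collection rule kept out of the data.

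**Working it through.** The point turns on wording. The protocol states no figure for it and no formula applies, so the check is to follow each type of event in a subject through sections 10.1 and 10.2.

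| Event in a subject | 10.1, first paragraph | 10.1, other paragraphs | 10.2 | Result |
|---|---|---|---|---|
| Serious, not device-associated | Exempt from the exclusion | UADE form, immediate report | Not applicable | Consistent |
| Serious, device-associated | Exempt from the exclusion | UADE form, which also captures device information; immediate report | 10.2.1 defines the unanticipated ones | Consistent |
| Non-serious, not device-associated | Progress notes only; not collected or analyzed | Last paragraph: UADE form and immediate IRB report | Not applicable | Contradictory |
| Non-serious, device-associated | Outside the section heading; if it applies, progress notes only | Last paragraph reaches it by its wording, though not by the heading | 10.2.1 covers serious events only; 10.2.2 gives no step for subjects | Undetermined |

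The next step is to ask what the study data would hold for the two non-serious rows under each available reading.

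1. **The first paragraph governs.** Events sit in progress notes and are not in the data. No summary is possible.
2. **The last paragraph governs.** Every non-serious event is put on a form intended for serious and unanticipated device effects and goes to the IRB at once. A record exists, but the first paragraph has been overridden.
3. **Both apply, with collection meaning the study dataset and reporting meaning the medical record and the IRB.** A form exists for each event, but the events are still outside the dataset and no summary is planned.

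The three readings give different records, and the protocol offers nothing to choose between them. Section 9.3 does not help: it limits the study report to what is needed to demonstrate the analgesic phenomenon and names no safety summary.

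**The case against.** Several points on the other side are sound.

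- **Serious events.** A reader might infer that safety as a whole cannot be reported under this protocol. The documents do not support that. Serious events have one route, and nothing in 10.1 or 10.2 contradicts it.
- **Subjects' device events.** A reader might infer that these have no route at all. That also goes too far. The all-events sentence at the end of 10.1 reaches them on its face, even though it sits under a heading that excludes them. Section 10.3, on the sponsor contact for serious events, is listed in the table of contents but its text is not in the copy reviewed, so it cannot be counted as missing.
- **Death.** It is absent from the list of serious outcomes in 10.1. The catch-all for other serious events would capture it, and 10.2.1 names device-associated death. This is a drafting slip with no practical effect.
- **Reconcilable readings.** Collection can be taken to mean the study dataset, and the IRB report is qualified by the board's own policies. This narrows the conflict but does not remove it. The last paragraph still calls for a UADE form for every event, where the first asks only for a progress note.
- **Tolerability.** Intra-operative VAS marks, hand raises and an overall VAS rating are recorded (section 4.1), so pain during the procedure is captured. The stated objective is analgesia, not safety. It would be wrong to say the trial learns nothing about tolerability.
- **Sponsor's choice.** A sponsor may decide to collect serious events only, and tabulation is often left to a statistical analysis plan. Both are true. The defect is that the protocol states that choice and its opposite in the same section.

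**Conclusion.** The point holds for non-serious adverse events in subjects and no further. Section 10.1 contradicts itself on how they are recorded and reported, and 10.2.2 does not resolve the matter for device-associated ones. Whether they are captured and can be summarized is undetermined.

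No numerical size can be given. The protocol states no expected event rate and lists no specific non-serious harms, so none is assumed here. An upper bound for zero observed events among 48 patients could be calculated, but it would be the same for any trial of that size and would not measure this defect. The ambiguity applies to every patient and both preparations in each. The efficacy comparison is unaffected.

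The conclusion rests on the text of sections 10.1, 10.2.1 and 10.2.2 as shown. An unseen statistical analysis plan could add a safety table but would not change the collection rule. The point deserves correction because it concerns patient-safety records in a procedure described as experimental and costs little to repair.

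**What to change.** Reconcile the passages into one rule.

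1. In the first paragraph of 10.1, delete the clause saying that events "will not be collected or analyzed unless considered serious by the Investigator". In the last paragraph, delete the remark that there should be no such events.
2. State that all adverse events in subjects, serious or not and device-associated or not, are recorded on the CRF, identified by tooth and procedure, and summarized in the study report. Identification by tooth and procedure suits the design, in which each patient has one preparation with preconditioning and one without. Adjust section 9.3 so that the report includes this summary.
3. Keep the UADE form and the immediate IRB route for events that meet the SAE or UADE definitions, or whose reporting the IRB's policies require.
4. In 10.2.2, state that device-associated events in subjects follow the same rule, and keep the existing staff route beside it.
5. As a minor wording repair, add death to the list of serious outcomes in 10.1.

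The cost is protocol wording, one adverse event log page in the CRF and one summary table. Sample size, procedures and the VAS analysis do not change.
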